5.6. Safety Analyses

All safety analyses except DLTs will be performed considering all treated population, summarized by dose level. The DLT analysis will be based on DLT-evaluable Population.

5.6.1. Extent of Exposure

5.6.1.1. Administration of Study Drug

The following parameters will be summarized. These will also be summarized by dose group.

- Duration of treatment
- Number of patients with treatment duration (<1 months, >=1-3 months, >=3-6 months, >=6-9 months, >9 months)
- Cumulative Dose
- Number of Cycles Treated
- Dose intensity
- Relative dose intensity (RDI)

Duration of treatment will be calculated as: (Date of last dose – Date of first dose + 1). For categorical summary, 1 month is set as 30.4375 days.

Cumulative dose

Cumulative dose (mg) is sum of the doses administered to a patient during the treatment period.

Dose intensity

Dose intensity (mg/day) is the cumulative dose (mg) divided by the duration of treatment (days).

Relative dose intensity (RDI)

Relative dose intensity (%) is calculated as cumulative dose (mg) divided by total planned dose (mg), where total planned dose is the treatment duration multiplied by planned dose level.

A by-patient listing of dose of study drug will also be provided.

5.6.1.2. Modification of Study Drug

The following drug modification will be summarized:

- The number and percentage of patients with at least one dose reduction along with reason for the reduction

- The number and percentage of patients with at least one dose interruption and reason for the dose interruption
- The number and percentage of patients with at least one dose error and reason for the dose error
- The number and percentage of patients with at least one dose missed and reason for the dose missed
- Number of dose reductions (1, 2, >2)
- Number of dose interruptions (1, 2, >2)
- Number of dose errors (1, 2, >2)
- Number of doses missed (1, 2, >2)

Listings of dose interruptions and dose reductions will be also provided.

5.6.2. Adverse Events

5.6.2.1. Deaths

Deaths and primary cause of death will be summarized for all deaths, deaths on treatment period, deaths within 30 days of last dose received, and deaths after 30 days of last dose.

A by-patient listing of all deaths/autopsy records will be provided for all treated Patients population.

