Adverse events	X	X	X						X	(X)	From signing ICF through 30-day safety follow-up or until start of new anticancer therapy, whichever is earlier. See Section 10.1 (X) only related SAE Investigator becomes aware of
Concomitant medications	X	X	X						X		From signing ICF through 30-day safety follow-up or until start of new anticancer therapy, whichever is earlier. See Section 6.4
ECOG Performance Status	X		X			X		X	X		

PK sampling		See Table 13 / Table 14									Table 13 for QD dosing / Table 14 for BID
Central ECG		See Table 13 / Table 14									To be performed as triplicates. For patients in Part A1 only. See Section 7.1.2
Local ECG ^c	X		X			X		X	X		12-lead ECG. Not needed if central ECG done the same day. Additional ECG monitoring as clinically indicated. See Section 7.1.2
Echocardiography/ MUGA	X							X			From Cycle 4 onwards, every 4 cycles or as clinically indicated. See Section 7.1.3
cfDNA blood samples			X			X		X	X		From Cycle 3 onwards, every other cycle. After 12 months, every 3 cycles.
Tumor tissue samples	X					(X)			(X)		Baseline sample optional for patients in Part A1. See Section 11.2 (X) On-treatment biopsy optional; can be done at one of these timepoints
Radiologic tumor assessment	X		X						(X)	(X)	Every 6 weeks (±7 days) from C1D1 irrespective of cycle. After 12 months, every 9 weeks (±7 days). (X) Patients who discontinue study treatment without radiographic PD will continue every 9 weeks (±7 days) until radiographic PD. See Section 7.1
Survival status										X	Every 3 months (±2 weeks); collect also further anticancer therapies. See Section 7.1 . For patients in Part A2 and B only
Administration of TAS3351		X	X								Continuous dosing See Section 6.1

^a PK lead-in period applies to Part A1 only: During PK lead-in period, patients will receive a single dose of TAS3351 3 days prior to the start of multiple TAS3351 dosing in Cycle 1 with subsequent PK blood collection. The PK blood sample collection times during the PK lead-in period may be found in [Table 13](#). For these patients, 72-hour post-dose assessments occur on C1D1, prior to C1D1 dosing.

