Echocardiography/MUGA	Baseline echocardiography/MUGA (multi-gated acquisition scan) is required. Left ventricular ejection fraction (LVEF) monitoring is needed every 4 cycles during TAS3351 treatment, and as clinically indicated. LVEF can be assessed by ECHO or MUGA; same modality should be used for a patient at screening and after dosing. See Section 7.1.3.
Hematology	Red blood cell (RBC) count, hemoglobin, hematocrit, platelets, white blood cell (WBC) count with differential: neutrophils (ANC), lymphocytes, monocytes, eosinophils, basophils. See Section 7.1.4.
Serum chemistry	AST, ALT, ALP, total bilirubin, direct bilirubin, albumin, LDH, triglyceride, total cholesterol, creatinine, BUN, Na, K, Cl, Ca (corrected value), Mg, blood glucose, C reactive protein (CRP), lipase, amylase, creatinine clearance (if there is a measured value, use the measured value) or eGFR. See Section 7.1.4. For a calculated CrCl value, use the Cockcroft-Gault formula: Male: $\text{CrCl} = \frac{(140 - [\text{insert age in years}] \times [\text{insert weight in kg}])}{72 \times [\text{insert serum creatinine in mg/dL}]}$ Female: $\text{CrCl} = \frac{(140 - [\text{insert age in years}] \times [\text{insert weight in kg}])}{72 \times [\text{insert serum creatinine in mg/dL}]} \times 0.85$
Coagulation	PT-INR, APTT, and fibrinogen. See Section 7.1.4 .
Urinalysis	Urine protein (qualitative), sediment, occult blood by dipstick or laboratory. If urine protein is 2+, add urinary β 2-microglobulin and quantitative measurement of proteinuria (24-hour urine collection for protein preferred). See Section 7.1.4.
Pregnancy test	For all female patients of childbearing potential: Serum or urine human chorionic gonadotrophin (human chorionic stimulating hormone) test (see the local regulation and/or CTFG recommendations). For screening, serum test required.
ECOG performance status	See Oken et al. for details. ²⁷
Efficacy and other	
Efficacy assessments	Efficacy assessment by tumor imaging. See Section 7.1.1.
Survival follow-up	Patient or family should be contacted for survival follow-up until withdrawal of consent, death, or loss to follow-up, until study completion. This should also include further anti-cancer treatments administered.
PK blood sampling	See Section 8.1 and Laboratory Manual.
Pharmacodynamic biomarker sampling	See Section 11.

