10.3.3. Reporting of Deaths (within 24 hours)

All deaths from the time the ICF is signed through the Safety Follow-up period (30 days after the last dose of study treatment or discontinuation, whichever is earlier) need to be recorded on the death page of the eCRF. Deaths, including death due to disease progression, if related to study drug, occurring from the time the ICF is signed through the Safety Follow-up period (30 days after the last dose of study treatment or discontinuation, whichever is earlier) must be reported immediately as SAEs and should not exceed 24 hours from the time the Investigator first becomes aware of the death. The primary cause of the death should be reported as the SAE term, if available, and entered on the death page of the eCRF.

When reporting a death, the Investigator will be required to identify which of the following best describes the category of death:

- Toxicity caused by adverse event
- Disease progression
- Clinical disease progression
- Other causes

Death is not an acceptable SAE term; death is an outcome of an SAE. Only if cause of death is not immediately known can death be reported as the SAE term. In those instances, the cause of death must be reported once obtained upon follow-up.

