5. STATISTICAL ANALYSIS

5.1. General Methods

Unless otherwise noted, the bulleted titles in the following subsections describe tabulations of discrete variables, by the frequency and proportion of patients falling into each category, grouped by dose level (with total). Summary table will be separated by part A1, part A2, part A and part B. Total of part A and part B will be added in disposition summary, study drug medication summary and overview of adverse events. All listings will be presented for part A and part B. Percentages given in these tables will be rounded and, therefore, may not always sum to 100%. Continuous variables will be summarized by treatment group (with total) using the mean, standard deviation, median, minimum, and maximum values.

Time to event distribution (i.e., PFS, OS and duration of response) will be estimated using Kaplan Meier techniques. Median survival time along with 95% CI will be constructed based on a log-log transformed CI for the survivor function $S(t)$. Rates at fixed time-points (e.g., PFS at 6 months) will be derived from the Kaplan Meier estimate and corresponding confidence interval will be derived based on Greenwood formula for variance derivation and on log-log transformation applied on the survivor function $S(t)$.

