5.5.7. Overall Survival (OS)

Overall survival is defined as the time from the date of first dose to the date of death due to any cause. For patients without documentation of death, the OS will be censored at the last contact date the patient was known to be alive. [Table 7](#) summarizes event and censoring rules for OS.

Table 7: Event and Censoring Rules for OS

Event/Censor	Decision	Date of event or censor to consider for analysis
Death	Event	Date of death
Patient alive without documented death	Censor	Date of last contact*

* Maximum date among completed dates relative to patient's information

In the absence of death confirmation or for patients alive as of the data cut-off date, survival time will be censored at the date of patient last known alive, or the data cut-off date, whichever is earlier. The patient last known alive is defined as the latest among dates recorded on eCRF.

Secondary Analysis in Part A (Patients in part A2 only), B

The Kaplan-Meier method will be used to estimate the median and percentile with the 2-sided 95% CI calculated using the Brookmeyer and Crowley method.

Kaplan-Meier plot will be provided.

End of safety follow-up data, survival follow-up data, and post study treatments data will be presented in by-patient listings.

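### The pooled Part A death table mixes patients with and without survival follow-up, so deaths more than 30 days after the last dose tend to look more frequent at backfilled doses

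*SAP*

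**What the plan says.** **What is tabulated.** SAP 5.6.2.1 states: "Deaths and primary cause of death will be summarized for all deaths, deaths on treatment period, deaths within 30 days of last dose received". The list of summaries ends with "deaths within 30 days of last dose received, and deaths after 30 days of last dose", and a by-patient listing of all deaths is added. No line is restricted by study part.

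**How it is laid out.** SAP 5.6 states: "All safety analyses except DLTs will be performed considering all treated population, summarized by dose level". SAP 5.1 adds: "Summary table will be separated by part A1, part A2, part A and part B". A by-dose death table for A1 and A2 combined is therefore planned alongside the separate ones.

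**Who is followed for survival.** In the Phase 1 Schedule of Events (Protocol Table 1), the survival status row has contacts every 3 months and carries the note "For patients in Part A2 and B only". Protocol 10.3.3 sets the window in which the death page must be completed: "All deaths from the time the ICF is signed through the Safety Follow-up period", that is, to about 30 days after the last dose. In SAP 5.5.7, OS is a "Secondary Analysis in Part A (Patients in part A2 only), B".

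**Text that names no part.** Protocol Table 12 says: "Patient or family should be contacted for survival follow-up until withdrawal of consent, death, or loss to follow-up, until study completion". Protocol Table 4 and SAP Table 2 also define the Survival Follow-up Period without limiting it to any part.

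**The concern.** Call a death late if it falls more than 30 days after the last dose. Under the Table 1 note, late deaths are actively sought in A2 and B and not in A1. An A1 patient who died late without the site learning of it still counts in the table's denominator and is in effect shown as not having died. The SAP respects this limit for OS, which it confines to A2 within Part A, but it does not carry the limit over to the death table, which counts the same event.

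The mix of the two rules varies with dose. Backfill goes only to selected dose levels, up to 10 patients at each (Protocol 4.2.1), and its stated purpose is to inform the RP2D. In the pooled columns, the doses under closest consideration hold the most patients with complete ascertainment, and the other doses hold few or none. A reader comparing late deaths across doses would then see a difference that comes partly from who was followed.

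**Working it through.** The plan gives no figure for the death summaries, so there is nothing to reproduce. The check is an illustration with the same true mortality at every dose.

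**Inputs**
- From the Protocol: up to 10 A2 patients at a backfilled dose (4.2.1); at least 3 and at most 15 A1 patients per dose (6.1.1); a 30-day window (10.3.3).
- Assumed, not in the documents: 6 A1 patients at the dose; exponential survival with median 12 months (range 8 to 18); follow-up of 6, 12 or 18 months; exponential time on treatment with median 4.5 months, borrowed from the 4–5 month chemotherapy PFS in Protocol 2.1.1; a share c of late A1 deaths becoming known.

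**Formulas.** Let λ = ln 2/12 = 0.0578 (death), μ = ln 2/4.5 = 0.1540 (stopping treatment), g = 30/30.4375 = 0.986 months, and F = length of follow-up. The true proportion dying late by F is

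L = e^(−λg) · μ/(λ+μ) · [1 − e^(−(λ+μ)(F−g))] − e^(−λF) · [1 − e^(−μ(F−g))]

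The true proportion dying by F is 1 − e^(−λF), and the remainder, E = 1 − e^(−λF) − L, is collected alike in A1 and A2. The table would be expected to show late deaths of:
- c·L at a dose with A1 patients only;
- (6c + 10)/16 · L at a dose with 6 A1 and 10 A2 patients.

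The gap is 10/16 · (1 − c) · L. It is the same for all deaths, because E is common to both doses.

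**Numbers at F = 12.** L = 0.9447 × 0.7273 × 0.9030 − 0.5 × 0.8167 = 0.620 − 0.408 = 0.212, and E = 0.500 − 0.212 = 0.288. With c = 0, the backfilled dose shows 10/16 × 0.212 = 0.133.

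| Follow-up | L | Late deaths, A1 only vs backfilled (c = 0) | All deaths, A1 only vs backfilled (c = 0) |
|---|---|---|---|
| 6 months | 0.069 | 0% vs 4% | 22% vs 27% |
| 12 months | 0.212 | 0% vs 13% | 29% vs 42% |
| 18 months | 0.340 | 0% vs 21% | 31% vs 52% |

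A simulation of 400,000 patients per scenario gave the same results.

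**Sensitivity**
- Half of late A1 deaths captured (c = 0.5), 12 months: 0.5 × 0.212 = 11% against 13/16 × 0.212 = 17%.
- All captured (c = 1): no gap; both doses show 21% late deaths at 12 months.
- Median OS 8 to 18 months and follow-up 6 to 18 months, c = 0: the gap runs from about 3 to 24 percentage points.
- Number of A1 patients at the dose, 12 months, c = 0: with 3, 10/13 × 0.212 = 16%; with 15, 10/25 × 0.212 = 8%.
- Unequal follow-up, c = 0: with 18 months for A1 and 6 months for A2, A1 shows 31% for all deaths and A2 shows 29%. The backfilled dose shows (6 × 0.306 + 10 × 0.293)/16 = 30%, so the gap in all deaths disappears.

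**The case against.** The case for leaving the plan alone has several parts.

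- **Separate tables are already planned.** Within the A1 table, and within the A2 table, every dose follows one ascertainment rule. This stands, and it confines the problem to the pooled Part A columns. It does not remove it, because the pooled table is planned as well.
- **A1 ascertainment does not stop at day 30.** A reader might infer that it does. Protocol 10.3.3 sets a mandatory window and does not forbid later entries. A1 patients who stop without radiographic PD continue scans every 9 weeks, and related SAEs that come to the investigator's notice are still reported (Protocol 5.5). This stands, so zero capture is the extreme case. However, the scans end at radiographic PD, so patients who have progressed are not reached this way.
- **Other text suggests that everyone is followed.** Protocol Tables 4 and 12 and SAP Table 2 name no part. The Table 1 note is more specific and agrees with the A2-only OS endpoint, so it probably governs. The conflict is still real, and sites could read it differently.
- **More deaths at backfilled doses are not guaranteed.** A reader might infer an excess whatever the drug does. The documents do not support that. Backfill opens only after a dose is judged safe in A1, so A2 patients tend to enter later, and shorter A2 follow-up can cancel the gap in all deaths. It does not restore the missing late A1 deaths.
- **No decision turns on this table.** No comparison of deaths between doses is planned, the RP2D rests on DLTs and the totality of data, and A1 and A2 differ in eligibility. This stands and limits the consequence. Differences in population are a further reason not to read late deaths across pooled doses.

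**Conclusion.** The point holds for the pooled Part A by-dose death table, and for two of its lines: all deaths and deaths after 30 days. There, late deaths are understated for A1 patients, and the late-death proportion tends to look higher at backfilled doses when true mortality is equal. On-treatment deaths and deaths within 30 days are collected alike and are not affected.

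Under the assumptions above (median OS 12 months, equal follow-up, 6 A1 against 6 A1 plus 10 A2 patients, no late A1 capture), late deaths show 0% against 4% at 6 months and 0% against 13% at 12 months. With half of late A1 deaths captured, the 12-month figures are 11% against 17%. A reader might posit that 40% of patients die late and arrive at 0/6 against 4/16, or 25%. The documents give no such proportion, and the illustration gives 7% at 6 months and 21% at 12 months. SAP 4.3.2 places the Part A analysis no later than 6 months after the last Part A patient is enrolled, so the shorter horizons matter for late entrants.

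This concerns how a safety table is presented. It does not touch DLT evaluation, ORR or OS, but it is worth correcting because the correction is cheap.

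**What to change.** 1. In SAP 5.6.2.1, limit the pooled Part A by-dose death table to on-treatment deaths and deaths within 30 days of the last dose.
2. Show all deaths and deaths after 30 days only in the separate A1, A2 and B tables. Footnote the A1 table to say that deaths after Safety Follow-up were not systematically collected.
3. Keep the by-patient listing of all deaths, so that no known death is lost from the report.
4. Reconcile Protocol Table 4, Protocol Table 12 and SAP Table 2 with the Table 1 note, so that all four say the same about survival follow-up in A1.

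The cost is SAP wording, one table shell, one footnote and a consistency edit. No new data are needed. The downside is two fewer lines in the pooled Part A table.

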5.6.2.2. Adverse Events

An AE is any untoward medical condition that occurs in patients while participating in this clinical trial. AEs will be coded according to the MedDRA (Version 25.1 or later) terminology, and the severity of the toxicities will be graded according to NCI CTCAE Version 5.0. Unique instances of all AEs (that is, after duplicates have been eliminated and overlapping and contiguous occurrences of the same event (same PT) have been collapsed) will be summarized.

A treatment-emergent AE (TEAE) is defined as an AE that is starting or worsening at the time of or after the first dose of study drug administration and within 30 days after the last dose of study drug and does not necessarily have a causal relationship to the use of the study drug.

The following summary tables will be generated:

- As an overall summary, summary of TEAEs with the number and percentage of patients reporting TEAEs, Grade ≥ 3 TEAEs, Treatment related AEs (TRAEs), Grade ≥ 3 TRAEs, serious adverse events (SAEs), treatment related SAEs, TEAEs leading to study drug discontinuation, dose interruption and dose reduction, and TEAEs with outcome of death.
- Summary of TEAEs (50mg cohort, 100mg cohort, 200mg cohort, 300mg cohort, 500mg cohort, any grade, Grade ≥ 3) presented by SOC and PT.

- Summary of TRAEs (50mg cohort, 100mg cohort, 200mg cohort, 300mg cohort, 500mg cohort, any grade, Grade ≥ 3) presented by SOC and PT.
- Summary of TEAEs (any grade, Grade ≥ 3) presented by dosing cohort and descending frequency of PTs (sorted by any grade PTs)
- Summary of TRAEs (any grade, Grade ≥ 3) presented by dosing cohort and descending frequency of PTs (sorted by any grade PTs)

A by-patient listing of all reported AEs will be provided for all treated Patients population, and non-TEAE will also be provided by listing separately.

5.6.2.3. Adverse Events Leading to Discontinuation/Interruption/Reduction of Study Drug

AEs leading to drug discontinuation/interruption/reduction will be summarized:

- Summary of TEAEs leading to discontinuation of study drug (50mg cohort, 100mg cohort, 200mg cohort, 300mg cohort, 500mg cohort, any grade, Grade ≥ 3) presented by SOC and PT
- Summary of TRAEs leading to discontinuation of study drug (50mg cohort, 100mg cohort, 200mg cohort, 300mg cohort, 500mg cohort, any grade, Grade ≥ 3) presented by SOC and PT
- Summary of TEAEs leading to interruption of study drug (50mg cohort, 100mg cohort, 200mg cohort, 300mg cohort, 500mg cohort, any grade, Grade ≥ 3) presented by SOC and PT
- Summary of TRAEs leading to interruption of study drug (50mg cohort, 100mg cohort, 200mg cohort, 300mg cohort, 500mg cohort, any grade, Grade ≥ 3) presented by SOC and PT
- Summary of TEAEs leading to reduction of study drug (50mg cohort, 100mg cohort, 200mg cohort, 300mg cohort, 500mg cohort, any grade, Grade ≥ 3) presented by SOC and PT
- Summary of TRAEs leading to reduction of study drug (50mg cohort, 100mg cohort, 200mg cohort, 300mg cohort, 500mg cohort, any grade, Grade ≥ 3) presented by SOC and PT

A by-patient listings of TEAEs and TRAEs leading to discontinuation/interruption/reduction of study drug will also be provided separately.

5.6.2.4. Serious Adverse Events

Serious adverse events (SAE) will be summarized:

- Summary of Serious TEAEs (50mg cohort, 100mg cohort, 200mg cohort, 300mg cohort, 500mg cohort, any grade, Grade ≥ 3) presented by SOC and PT

- Summary of Serious TRAEs (50mg cohort, 100mg cohort, 200mg cohort, 300mg cohort, 500mg cohort, any grade, Grade ≥ 3) presented by SOC and PT

A by-patient listing of SAEs will also be provided.

5.6.2.5. Consolidated AEs

Consolidated terms of AEs will be summarized by treatment group for each category:

- Summary of TEAEs (50mg cohort, 100mg cohort, 200mg cohort, 300mg cohort, 500mg cohort, any grade, Grade ≥ 3) presented by category and PT
- Summary of TRAEs (50mg cohort, 100mg cohort, 200mg cohort, 300mg cohort, 500mg cohort, any grade, Grade ≥ 3) presented by category and PT
- Summary of serious TEAEs (50mg cohort, 100mg cohort, 200mg cohort, 300mg cohort, 500mg cohort, any grade, Grade ≥ 3) presented by category and PT
- Summary of serious TRAEs (50mg cohort, 100mg cohort, 200mg cohort, 300mg cohort, 500mg cohort, any grade, Grade ≥ 3) presented by category and PT

A by-patient listing of consolidated AEs will also be provided.

5.6.3. Dose-Limiting Toxicity (DLT)

Primary Analysis in Part A

Incidence of Dose-limiting Toxicity (DLT) will be summarized by DLT category (hematologic, hepatic, renal, skin, other nonhematologic, other) and DLT event and the analysis will be based on DLT-evaluable Population. The occurrence of any toxicity outlined in Table 8 of Protocol during the DLT evaluation period will be considered a DLT, excluding toxicities clearly related to disease progression or intercurrent illness (See Protocol Section 6.1.2).

A by-patient listing will also be provided.

